
animal models and has focused on the dysfunction side of the muscle plasticity continuum, with sparse attention given to measures to reduce VIDD [9-12, 15, 17, 26]. Only two studies have directly studied the impact of MV on human diaphragm structure and none have directly measured muscle contractile performance following periods of MV. Levine's recent report on the effects of 36 hours of MV in humans was discussed earlier. The only other human study used a case control design that qualitatively showed profound diaphragm muscle fiber atrophy in a young child ventilated for 47 days compared to a child ventilated for 3 days [27]. The current evidence indicates that short periods of MV leads to VIDD in animal models and difficult to wean humans clinically demonstrate VIDD. Given the evidence of VIDD, it is clear that mechanistic human data are needed to design strategies to prevent or treat the problem.

In this study, we propose to stimulate either the right or left human hemidiaphragm hourly during routine cardiothoracic (CT) surgery and to obtain diaphragm muscle biopsies from the stimulated and unstimulated hemidiaphragms at the end of surgery for analysis with micro gene arrays, mitochondrial function and single muscle fiber contractile properties. To our knowledge, this project would provide the first simultaneous data on the human diaphragm's gene expression, mitochondrial function and contractile responses to activity during surgery and MV support. This knowledge will be invaluable to developing strategies to protect the diaphragm from the deleterious effects of MV and surgery.

This project will help establish our human diaphragm surgery/MV model, facilitating applications for support from the NIH to study preoperative diaphragm training paradigms and intraoperative pharmacologic interventions.

5. Specific Aims:

Aim 1: Compare the expression of the human diaphragm genes that control energy metabolism, excitation-contraction coupling, contractile proteins and oxidative stress in stimulated and unstimulated diaphragm muscle samples.

Aim 2: Compare the single muscle fiber contractile characteristics (subdivided by muscle fiber type) of stimulated and control diaphragm muscle fibers.

Aim 3: Compare the mitochondrial function of stimulated and control diaphragm muscle fibers.

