We hypothesize that intermittent stimulation of either the right or left human hemidiaphragm during thoracic surgical procedures and lung transplant lasting approximately 5 hours or longer will prevent or attenuate inactivity-induced changes in gene expression, mitochondrial function and single fiber contractile properties as compared to the unstimulated hemidiaphragm.

6. Research Plan:

Subjects:

Patients undergoing regularly scheduled cardiothoracic surgery, including lung transplants, at Shands Hospital at the University of Florida will be recruited to enroll in this prospective study. From each subject an informed consent will be obtained to donate two diaphragm muscle biopsy samples during the surgery.

After recruitment, an initial evaluation consisting of basic demographic information as well as diagnostic information pertaining to the surgery will be performed before the scheduled surgery to search for exclusion factors. In addition, we will track medications, ventilator use, complications, and length of stay during the patient's hospitalization for surgery. Up to 100 subjects will be studied.

Exclusion Criteria:

1. Age < 18 or > 80,
2. history of prior surgery to the diaphragm or pleura;
3. a diagnosis of COPD will be determined from a clinical history consistent with chronic bronchitis and/or emphysema, a long history of cigarette smoking, and pulmonary function tests consistent with irreversible airflow obstruction (FEV1 < 40% predicted, according to European Respiratory Society criteria (1)).
4. a diagnosis of chronic heart failure (NYHA class IV) (2)
5. clinical diagnosis of other lung disease (cystic fibrosis, bronchiectasis, lung cancer; etc.);
6. renal insufficiency (serum creatinine > 1.6 mg/dl);
7. severe hepatic disease (any liver function tests > 1.5 times the upper limit of normal);
8. undernourishment (body mass index < 20 kg/m²),
9. chronic uncontrolled or poorly controlled metabolic diseases (e.g., diabetes, hypo- or hyperthyroidism)
10. orthopedic diseases, suspected paraneoplastic or myopathic syndromes,
11. if in the surgeons' judgment the patients' clinical status warrants, diaphragm stimulation will be stopped and biopsies will not be obtained,
12. items #3 and #5 above will not apply to transplant patients.

Experimental Procedure:

Before the surgery:

A pulmonary function test will be performed to determine whether the subject qualifies for the study.

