PFT: Subjects will complete a forced expiratory maneuver to determine eligibility for training. Tests will be completed according to American Thoracic Society guidelines,(3) and 3 to 5 trials administered, separated by 2 minutes of rest. If an individual demonstrates FEV1<40% of predicted, he or she will be removed from any further

participation in the study. An FEV_{1.0} of 40% or less of predicted as an exclusionary factor will not apply to transplant patients.

In addition, the qualified subjects will undergo maximum inspiratory pressure test before the scheduled surgery.

Maximal Inspiratory Pressure: Subjects will perform a maximal inspiratory pressure maneuver from residual volume, in accordance with American Thoracic Society testing guidelines.(3) Trials will be administered until 5% variability is achieved between three trials (typically achieved within 5 trials), and separated by a two-minute rest. A short rest between maneuvers will be provided to prevent muscle fatigue.

In conjunction with respiratory testing, we will monitor baseline and exertional blood pressure, heart and respiratory rate, and pulse oximetry. The following tests will be completed on all subjects.

During surgery following procedures will be performed,

Diaphragm stimulation: Either the right or the left hemidiaphragm will be stimulated during routine cardiothoracic surgical procedures. This will be decided by the surgeon on the basis of ease of access to the corresponding phrenic nerve. Rodent models of MV have shown that different neuromuscular blockers can exert varied effects on the diaphragm contractile properties (4-7). The right or the left hemidiaphragm will be stimulated via the corresponding phrenic nerve with a temporary cardiac pacer (Medtronic 5388) with wire electrodes. The surgeon will identify the phrenic nerve on the pericardium and the pacing electrodes will be sutured to the pericardium immediately adjacent (~8 mm) to either side of the phrenic nerve (8). It is not necessary for the pacing electrodes to touch the phrenic nerve to stimulate the phrenic nerve and generate a hemidiaphragm contraction.

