[name] has observed vigorous left hemidiaphragm contractions on many occasions during temporary heart pacing when electrodes were applied to the pericardium close to the left phrenic nerve. Great care will be taken to ensure that the stimulating electrodes do not contact the phrenic nerve. The left phrenic nerve will be stimulated near the pulmonary artery to prevent pacing the heart. The right phrenic nerve will be stimulated on the right side of the pericardium.

Patients receive non-depolarizing neuromuscular blockers during surgery to prevent limb muscle contractions. The diaphragm is more resistant to neuromuscular blockade than limb muscles, and remains responsive to stimulation despite neuromuscular blockade sufficient to temporarily paralyze limb muscles (9, 10). The surgeon will select the hemidiaphragm for stimulation depending upon the ease of access to the corresponding phrenic nerve. There is no evidence that the muscle fiber contractile characteristics or gene expression differ between the right and left human hemidiaphragms.

Once the electrodes are sutured in place, the stimulator will be activated with the lowest possible current. The stimulator current will then be systematically increased until a vigorous contraction of the corresponding hemidiaphragm is observed, which will be

termed the threshold stimulus. The stimulus intensity will be adjusted to three times the threshold level for subsequent stimulation. The hemidiaphragm on the unstimulated side will be observed to verify that it is not entrained with the hemidiaphragm contractions on the stimulated side. Stimulation will be conducted for one minute (30 pulses per minute, 15 msec duration) either 30 or 60 minutes following initiation of MV and every 30 or 60 minutes thereafter. The frequency of stimulation (every 30 or 60 minutes) will be determined by the estimated duration of surgery. In order for both human hemidiaphragms to generate contractions, stimulation must be applied to both phrenic nerves or hemidiaphragms (11). The temporary wire electrodes that are used for the electrical stimulation will be removed at the end of the surgery.

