The method selected to obtain diaphragm biopsies was designed to minimize the risk of bleeding, phrenic nerve injury, or diaphragmatic impairment. The surgeon will obtain a full-thickness diaphragm sample, approximately 6 mm X 20 mm, from the antero-lateral costal regions of the stimulated and unstimulated hemidiaphragms, shortly before the surgery is completed. By harvesting the diaphragm biopsy from the anterior costal diaphragm, in a region opposite of the phrenic nerve insertion, we will minimize the proximity to phrenic insertion. The wounds will be closed with sutures. The surgeon will place the biopsy samples on ice and hand them to study staff. Tissue samples will be divided using the procedures described below. One part of the sample will be sent to [name]'s laboratory for mitochondrial respiration and gene analysis. One sample will be sent to [name] laboratory (University of Florida, College of Medicine) for RNA analysis. Samples to be analyzed with micro gene array and RNA analysis will be immediately placed in RNAlater solution and stored at -80° C until analysis. Another part of the sample will be sent to [name] laboratory (College of Health and Human Performance, University of Florida) for contractile and fiber type measures. Samples destined for single fiber contractile properties will be placed in a relaxing solution containing 50% glycerol (vol/vol) and stored at 20°C for no more than 4 wk before subsequent analysis. (12) A portion of the tissue samples will be sent to a non-UF investigator, [name] at the University of Arizona for

analysis of muscle titan integrity. After harvest, tissue samples will be coded to protect subject confidentiality and tissue samples will not contain identifying information such as the subject name, medical record are other identifying information. All of the tissue will be consumed during the analysis of the various variables and will not be stored or bank for use outside of this protocol.

In addition we will request the subject's permission to be videotaped for this research project. The process of stimulation of the phrenic nerve and the contraction or movement of the diaphragm muscle will be videotaped during the surgery. A separate consent [Consent to be videotaped and to different uses of the videotape(s)] will be obtained from the subjects.

C. After Surgery:

Data Analysis:

Microarray Analysis:

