Fibers will be retrieved from the relaxing solution and fiber bundles will be placed in a solution containing 1% Triton X-100 to permeabilize the plasma membrane for ~20 min, and dissected under a dissecting microscope. Single fibers will be transferred from the skinning solution to a relaxing solution (pCa 9.0) for force measurements. Force measurements will be performed in solutions containing the following (in mM): 10.0 EGTA, 1.0 free Mg²⁺, 5.0 MgATP, 15.0 creatine phosphate, 50.0 imidazole, 2.0 DTT, and PCK at 1 mg/ml with a total ionic strength of 150 mM. The relaxing solution will have pCa of 9.0, and the activating solution a pCa of 4.0. Fiber ends will be fixed by exposing them to a 5% glutaraldehyde solution to maintain noncompliant attachments of the fibers to a force transducer and servo-controlled motor. Fibers will be mounted horizontally on two small stainless steel hooks in a temperature-controlled flow-through acrylic chamber located on the stage of an inverted microscope. Fibers will be attached at one end to a force transducer (resonant frequency of 5 kHz), and the other end to a servo-motor (step time: 800 μ s). Sarcomere length will be set at 2.5 μ m and monitored by first-order laser diffraction. Signals will be recorded with a custom-designed LabView-based software and a data acquisition board. Fiber dimensions will be measured to calculate fiber cross-sectional area. A baseline force measurement will be obtained while fibers are perfused with a pCa 9.0 solution. The perfusate will be switched to a pCa 4.0 solution (in the same flow-through chamber) to maximally activate the fibers, and after maximal activation is achieved, the fiber will again be perfused with a pCa 9.0 solution to verify that force returns to its original baseline level. Maximum specific force (N/cm²) will be calculated by dividing the maximum isometric force by fiber cross-sectional area. Approximately 4 fibers of each fiber type will be analyzed. This technique has been previously reported in greater detail. (15)

Mitochondrial function measurements in diaphragm muscle:

Elevated levels of oxidative stress produced during mechanical ventilation (MV) directly contribute to diaphragmatic atrophy and contractile dysfunction, thus preventing the successful removal of patients from the ventilator (i.e. "weaning") (16, 17). Numerous lines of evidence (18, 19) have surfaced implicating reactive oxygen species (ROS) and

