mg/ml NTB (nitrotetrazolium blue). Complex II: 4.5 mM EDTA, 10 mM KCN, 0.2 mM phenazine methasulfate, 84 mM succinic acid and 50 mM NTB in 1.5mM phosphate buffer, pH 7.4. Complex IV: 5 mg 3:30-Diamidobenzidine tetrahydrochloride (DAB) dissolved in 9 ml phosphate buffer (0.05 M, pH 7.4), 1 ml catalase (20 µg/ml), 10 mg cytochrome c, and 750 mg sucrose. Complex V: 35 mM Tris, 270 mM glycine, 14mM MgSO₄, 0.2% Pb(NO₃)₂, and 8 mM ATP, pH 7.8. Gels will be washed in distilled water and the bands quantified by digital imaging using a CCD camera. Activity and content will be normalized to muscle weight, mitochondrial DNA content (21) as well as citrate synthase activity (22).

3. Titan analysis: The integrity and phosphorylation of Titan subunits of the sarcomere will be analyzed in [name] laboratory at the University of Arizona. [name] group has extensive experience making this unique measurement and will follow procedures as they have previously published.(25, 26)

Statistical Analysis:

We will use a mixed effects model with random intercept for each subject to evaluate the fixed effects of stimulation and fiber type on single-fiber force mechanics. For other dependent variables (i.e. mitochondrial respiration, RNA, protein quantification), we will test differences between the stimulated and unstimulated tissue samples using paired parametric T tests when the data meet the assumptions of parametric analysis, or non-parametric tests if the data are not normally distributed.

7. Possible Discomforts and Risks:

The risks of diaphragm biopsy include failure of the biopsy site to close, bleeding, phrenic nerve injury, and diaphragm dysfunction. The portion of the diaphragm from which the biopsy is obtained (6 mm by 20 mm section of tissue) will be isolated from the remaining muscle by surgical staples, prior to excision of the full-thickness biopsy sample. The site will also be reinforced with sutures, minimizing the risks of bleeding or failure of the biopsy site to close.

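### The single-fiber force model has only a subject intercept, so if a subject's two biopsies differ beyond fiber-to-fiber variation, the Aim 2 stimulation effect is tested against too small an error

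*Combined protocol and SAP*

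**What the plan says.** The only analysis given for single-fiber force is a "mixed effects model with random intercept for each subject to evaluate the fixed effects of stimulation and fiber type on single-fiber force mechanics" (section 6, Statistical Analysis). Aim 2 is to "Compare the single muscle fiber contractile characteristics (subdivided by muscle fiber type) of stimulated and control diaphragm muscle fibers" (section 5).

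The data structure comes from other parts of section 6:

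- **Subjects:** each patient consents to "donate two diaphragm muscle biopsy samples during the surgery".
- **Diaphragm stimulation:** "Either the right or the left hemidiaphragm will be stimulated during routine cardiothoracic surgical procedures".
- **Diaphragm Biopsies:** the samples come "from the antero-lateral costal regions of the stimulated and unstimulated hemidiaphragms", shortly before the operation ends.
- **Single-fiber mechanical measurements:** "Approximately 4 fibers of each fiber type will be analyzed". Whether this is per biopsy or per subject is not stated, nor is the number of fiber types.

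Nowhere does the plan add a biopsy-level random effect, a random stimulation slope, robust standard errors, or averaging of fibers before the force comparison. For the other outcomes, the same paragraph compares stimulated and unstimulated samples by paired t tests, or by non-parametric tests that it does not describe as paired.

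**The concern.** All fibers from one biopsy share one stimulation status. However many fibers are measured, each subject contributes one stimulated-versus-unstimulated pair. The subject intercept cancels from that contrast, so it removes neither of two further sources of variation: differences between a subject's two biopsies from sampling, handling or assay, and differences between subjects in their response to stimulation. In the stated model both fall into the fiber residual, and stimulation is tested with fiber-level degrees of freedom.

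If either source is present, confidence intervals for the effect on force are too narrow and p-values too small. Aim 2 could then report a contractile benefit that is only biopsy-to-biopsy noise. If both are absent the model is valid, but as written it has no term that would show which case holds.

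**Working it through.** The plan gives no power, standard deviation, significance level or derived sample size for force, so there is no figure to reproduce. The question is how the error rate of the stated model depends on the missing variance component.

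**Inputs from the documents.** Two biopsies per subject; about 4 fibers per type; up to 100 subjects; one random intercept per subject.

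**Assumed inputs.** Two-sided 5% level. Two or three fiber types (T). Either 4 fibers of a type per biopsy, or 2 if the stated 4 is per subject. Between-biopsy share of within-subject variance, ρ, from 0 to 0.20.

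**Formulas.** Scale within-subject variance to 1, with biopsy variance ρ and fiber variance 1−ρ. Let m be fibers of one type per biopsy and M = T×m all fibers per biopsy. The subject-only model pools the subject-by-side mean square (n−1 df) with the fiber-level mean square (2n(M−1) df). Its residual therefore has expectation close to (1−ρ) + Mρ/(2M−1). The ratio of true to assumed variance is

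- overall effect: R = [(1−ρ) + Mρ] / [(1−ρ) + Mρ/(2M−1)]
- effect within one type (interaction in the model): R = [(1−ρ) + mρ] / [(1−ρ) + Mρ/(2M−1)]

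Type I error = 2[1 − Φ(1.96/√R)]. The true standard error is √R times the reported one.

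**Worked case, ρ = 0.10, m = 4, T = 2, M = 8.** The denominator is 0.90 + 0.8/15 = 0.953.

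- Overall: R = (0.90 + 0.80)/0.953 = 1.783, √R = 1.34, error 14.2%.
- Within type: R = (0.90 + 0.40)/0.953 = 1.364, √R = 1.17, error 9.3%.

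**Type I error (%) over the assumed range**

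| Effect | Fibers per biopsy | ρ=0 | 0.05 | 0.10 | 0.20 |
|---|---|---|---|---|---|
| Within one type | 4 of that type | 5.0 | 7.1 | 9.3 | 14.0 |
| Within one type | 2 of that type | 5.0 | 5.8 | 6.8 | 8.7 |
| Overall | 4 in total | 5.0 | 7.1 | 9.3 | 13.8 |
| Overall | 6 in total | 5.0 | 8.3 | 11.8 | 18.6 |
| Overall | 8 in total | 5.0 | 9.6 | 14.2 | 22.8 |
| Overall | 12 in total | 5.0 | 12.0 | 18.7 | 29.7 |

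Two and three fiber types give the same within-type rates to about 0.1 point. At ρ = 0.01 the within-type rate is 5.2–5.4%. At ρ = 0.05, 0.10 and 0.20, the standard error is too small by a factor of 1.09, 1.17 and 1.33 (within type, 4 fibers), 1.04, 1.07 and 1.15 (within type, 2 fibers), or 1.18, 1.34 and 1.63 (overall, 8 fibers).

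**Simulation check.** Balanced simulations at 10, 20, 50 and 100 subjects gave, at ρ = 0.05, 0.10 and 0.20:

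- overall, 8 fibers: 9.2–9.6%, 13.9–14.2% and 21.9–23.2%
- within type, 4 fibers: 6.9–7.4%, 9.0–9.6% and 13.5–14.8%

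The rates barely change with the number of subjects. Paired analyses of biopsy averages stayed at 4.5–5.4%. Unbalanced REML fits (20 subjects, 2 types, 2–6 fibers per type per biopsy) at ρ = 0, 0.05, 0.10 and 0.20 gave 5.3, 9.8, 14.5 and 23.0% for the overall effect. The paired analysis by type gave 5.2, 4.9, 5.0 and 4.7%.

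**Is one biopsy intercept enough for the by-type question?** Not if biopsy variance differs by type. With 20 subjects, 4 fibers of each of 2 types, biopsy variance of 10% and biopsy-by-type variance of 5% or 10%, the interaction test with a single biopsy intercept rejected a true null 7.2% or 9.8% of the time. The same test on paired differences rejected 5.0% or 5.1%.

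**The case against.** The strongest reply is that the missing variance may be negligible. Both samples come from the same costal region at the same stage of surgery, and the protocol states that "There is no evidence that the muscle fiber contractile characteristics or gene expression differ between the right and left human hemidiaphragms". If ρ is near zero the stated model holds its level, and with 2 fibers of a type per biopsy the inflation is modest even at ρ = 0.05. This stands as a limit on size: the 20–30% rates need ρ = 0.20 and 8 to 12 pooled fibers, none of which the documents establish. It does not remove the defect. The right-left statement concerns a systematic side difference, not random variation between biopsies. Storage is allowed "for no more than 4 wk before subsequent analysis" under Diaphragm Biopsies and for up to 3 weeks under Muscle fibers treatment, and neither section says whether a subject's two samples are assayed together. That silence does not show they are assayed apart, but it leaves zero variance as an unsupported assumption.

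Three narrower points also have weight:

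- The within-type rates assume a stimulation-by-type interaction, which the Statistical Analysis paragraph does not state. Read literally, it has main effects only, and the overall rates apply.
- A response that varies between subjects cannot create a false positive if stimulation does nothing in anyone. It matters for the interval around an average effect. The false-positive argument rests on biopsy variance.
- The plan sets no significance level or primary endpoint, so 5% is an assumed standard.

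These qualify the figures. They do not change the direction of the error.

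**Conclusion.** The concern holds. The stated force model tests stimulation against fiber-level error, although the design supplies one biopsy pair per subject. The omission is certain, and so is the direction of its effect if between-biopsy variance is above zero. The size is unknown. Over an assumed share of 5–20%, type I error at a nominal 5% runs from about 6–9% (one fiber type, 2 fibers per biopsy) to 12–30% (overall effect, 12 fibers per biopsy). At zero share there is no inflation. Enrolling more subjects does not cure it. The sampling design itself is sound. The analysis sentence should be corrected before the force data are analysed.

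**What to change.** Replace the force sentence in Statistical Analysis with text such as:

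> For the overall effect of stimulation, single-fiber force will be analysed with a linear mixed model with fixed effects of stimulation, fiber type and their interaction, random intercepts for subject and for biopsy (hemidiaphragm) within subject, and Kenward-Roger or Satterthwaite degrees of freedom. For the comparison by fiber type (Aim 2), fibers will be averaged per biopsy and type, and the stimulated and unstimulated averages will be compared by a paired analysis. The effect will be reported with its confidence interval and number of pairs for each type. Differences between types in the stimulation effect will be tested on the same paired differences.

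Name one of the two degrees-of-freedom methods in the final text. A biopsy-by-type random term is an alternative for the by-type part. Also state whether the figure of about 4 fibers per type is per biopsy or per subject.

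The change needs no new data and brings force into line with the paired t tests planned for the other outcomes. Its cost is some precision if the between-biopsy variance is truly zero:

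| Subjects | Interval widening: paired by type / nested overall (Satterthwaite) | Power for an effect with 80% under the stated model: paired / nested |
|---|---|---|
| 10 | 11% / 15% | 71–72% / 70% |
| 20 | 5% / 9% | 76% / 74–75% |
| 50 | 2% / 5% | 78–79% / 77% |

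In that case the nested overall test is also somewhat conservative: its type I error was 3.3% at 10 subjects and 3.7% at 20. A subject with no fibers of a given type on one side drops out of that type's pairs.

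### Aim 2 asks for the stimulation comparison by fiber type, but the single-fiber model names no stimulation-by-type term or within-type contrast, and its only random effect is a subject intercept

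*Combined protocol and SAP*

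**What the plan says.** Section 5 states Aim 2 as: "Compare the single muscle fiber contractile characteristics (subdivided by muscle fiber type) of stimulated and control diaphragm muscle fibers". The hypothesis that follows the aims is broader. It concerns "single fiber contractile properties as compared to the unstimulated hemidiaphragm" and does not mention fiber type.

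Under the single-fiber mechanical measurements in section 6, the sampling target is: "Approximately 4 fibers of each fiber type will be analyzed". The text does not say whether that count is per biopsy or per subject.

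The Statistical Analysis paragraph of section 6 has one sentence on this outcome. It begins "We will use a mixed effects model with random intercept for each subject" and gives the purpose as "to evaluate the fixed effects of stimulation and fiber type on single-fiber force mechanics". No model equation is given. Nothing in the document names an interaction, a stratified model, within-type contrasts, or a random effect for biopsy or side.

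On size, section 6 says only "Up to 100 subjects will be studied". There is no effect size, SD, alpha or power.

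**The concern.** The aim and the analysis do not match. The aim carries the qualifier "subdivided by muscle fiber type", and fibers are classified and counted by type. The model sentence, on its plain reading, has one coefficient for stimulation and one set of coefficients for type. Such a model imposes the same stimulation effect on every type.

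Two things are at stake. First, if stimulation acts mainly on one type, the reported effect is a diluted mixture whose size depends on how many fibers of each type were measured. Effects in opposite directions cancel. Because the plan does not fix the by-type analysis, the choice between pooled and by-type results could be made after the data are seen.

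Second, stimulation is applied to a whole hemidiaphragm, and each subject contributes one biopsy per side. A subject intercept absorbs differences between people but not differences between the two biopsies of one person. Any such difference unrelated to stimulation is then judged against fiber-to-fiber noise, which is too small a yardstick for the stimulation contrasts, whether common or within type.

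**Working it through.** The plan states no figure that could be reproduced, so the check is algebra plus illustration.

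**Inputs from the protocol:** the two named fixed effects, the subject random intercept, and about 4 fibers per type.

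**Assumptions not in the protocol:** two fiber types; m = 4 fibers per type per biopsy; fiber SD σ = 1; biopsy SD τ = 0.5, shared by both types; n = 20 subjects; two-sided 5% level.

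**Step 1. What an additive model estimates.** With the same number of fibers of each type on both sides, the stimulation coefficient is w1·δ1 + w2·δ2, where δ is the true effect in a type and w is that type's share of the fibers.

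- Shares 4:4, effects 0 and 0.6: 0.5×0 + 0.5×0.6 = 0.30.
- Shares 4:4, effects -0.4 and +0.4: 0.5×(-0.4) + 0.5×0.4 = 0.
- Shares 6:2, effects 0 and 1: 0.75×0 + 0.25×1 = 0.25. A small simulation gave 0.20 to 0.23 and a larger one 0.25.

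These results do not depend on any SD. With the interaction included, true effects of 0 and 1 were recovered as 0.01 and 1.01 at 100 subjects.

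**Step 2. Precision, with biopsy variation allowed for.**

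- Common effect: variance 2(τ² + σ²/2m)/n.
- Within-type effect: variance 2(τ² + σ²/m)/n.
- Interaction: variance 4σ²/(mn), since a biopsy effect shared by both types cancels.

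With τ = 0 these are 0.25/n, 0.50/n and 1.00/n, so the within-type variance is 2.0 times and the interaction variance 4.0 times that of the common effect. With τ = 0.5 they are 0.75/n, 1.00/n and 1.00/n, a ratio of 1.33 for both. Twice the variance is therefore the upper end for within-type estimates.

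With τ = 0 and 80% power (multiplier 1.96 + 0.84 = 2.80), the minimum detectable differences for common, within-type and interaction are 0.31, 0.44 and 0.63 fiber SDs at 20 subjects, and 0.14, 0.20 and 0.28 at 100. If the 4 fibers are per subject (2 per side), each is multiplied by 1.41. Biopsy variation makes the common and within-type figures larger.

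**Step 3. False positives with a subject intercept only.** Each subject has 16 fibers and so 15 within-subject degrees of freedom. One of these separates the two biopsies and has expected mean square σ² + 8τ² = 1 + 8×0.25 = 3. The other 14 have expected mean square 1.

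- Pooled residual variance: (14×1 + 3)/15 = 1.133.
- Standard error the model reports: √(2×1.133/(8×20)) = 0.119.
- True standard error: √(0.75/20) = 0.194.
- Effective cut-off: 1.96×0.119/0.194 = 1.20, so a true null is rejected about 23% of the time.

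The same formula gives 5% at τ = 0, 10% at τ = 0.25 and 42% at τ = 1. Both variances scale with 1/n, so recruiting more subjects does not cure it.

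**Step 4. Rejection rates (τ = 0.5, simulated).**

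| True effects; n | Mean common estimate | Additive model, subject intercept only | Biopsy-level: common | Biopsy-level: type II | Biopsy-level: interaction |
|---|---|---|---|---|---|
| 0, 0; 20 | 0 | 23% | 5% | 5% | 5% |
| 0, 0.6; 20 | 0.30 | 64% | 31% | 72% | 72% |
| -0.4, +0.4; 20 | 0 | 21 to 24% | 5% | 41% | 92 to 93% |
| 0, 0.6; 50 | 0.30 | 88 to 89% | 67% | 99% | 99% |

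The biopsy-level columns use paired side differences. The higher rates in the subject-intercept column are not better power: they include the inflation from Step 3. The rates of 31%, 5% and 67% for the common effect therefore describe a biopsy-level paired analysis, not the model as stated.

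**The case against.** The strongest reply is that the plan is silent rather than wrong. It gives no equation, and a two-factor model with interaction fits the same words. Aim 2 is itself a reason to read them so. This stands: a reader might infer that the model is additive as a matter of record, and the protocol does not say that. It does not remove the point, because a plan that intends an interaction should name it and the remedy is the same.

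Second, a reader might infer that the analysis cannot answer Aim 2 at all. That goes too far. Even an additive model gives the overall stimulated-versus-unstimulated contrast adjusted for type, which is what the hypothesis asks. Only the by-type part is left without an estimate.

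Third, nothing in the protocol predicts opposite effects in different types, so the cancelling case is a construction. If the effects are similar across types, the common effect is the more efficient estimate. Both statements are right, and the second is a reason to keep the common effect.

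Fourth, the biopsy random effect concerns clustering, not by-type estimation. It is a separate defect, but it belongs in the same revision: without it the new within-type intervals would be too narrow.

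**Conclusion.** The by-type part of Aim 2 has no stated analysis. Read as main effects only, the model returns one common stimulation effect weighted by the fiber mix. Effects that differ by type are then diluted or cancel, while the overall hypothesis remains testable. This follows from the model's form and rests on no assumed SD.

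The clustering problem depends on biopsies from one subject differing for reasons other than stimulation. The protocol gives no figure for this. Across assumed biopsy SDs from 0 to 1 fiber SD, the false-positive rate under a subject-only intercept runs from 5% to about 42%, with about 23% at 0.5.

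All power and rejection rates are illustrations under the listed assumptions. The protocol supports neither the claim that the plan rules out an interaction nor the claim that Aim 2 is wholly unanswerable. The change should be made: it lets the trial report what its own aim asks for.

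**What to change.** Revise the single-fiber sentence in the Statistical Analysis paragraph so that it:

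- includes fixed effects of stimulation, fiber type and their interaction;
- includes random effects for subject and for biopsy (side within subject);
- reports the stimulated-minus-unstimulated difference with a 95% CI within each fiber type, plus the interaction test;
- states whether the within-type contrasts and the interaction test are confirmatory or descriptive;
- keeps the common stimulation effect, adjusted for type, as the overall estimate for the hypothesis.

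It would also help to say whether the target of about 4 fibers per type is per biopsy or per subject.

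The cost is a few lines of text and no new data. Within-type estimates are less precise than the common effect, with 1.33 times the variance at a biopsy SD of 0.5 and up to twice with two balanced types and no biopsy variation. Honest allowance for biopsy variation will also widen the interval for the common effect compared with the model as now worded.
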